Statistical methods for the conventional analyses of primary efficacy endpoint will use a mixed effects model with repeated measures (MMRM) comparing placebo to the identified ED₉₀ dose from the Bayesian analysis. (revised per Amendment 09) The model will include randomization stratification variables; clinical subgroup (MCI due to AD, mild AD), the presence or absence of ongoing AD treatment (ie, AChEIs or memantine or both), *APOE4* status (positive, negative) and baseline ADCOMS as covariates. These analyses will be performed on the Full Analysis Set as well as the PP set based on the ITT principle. In case of early success, the conventional analyses will also be performed using the data collected prior to the IA. (revised per Amendment 01)

Analysis for the Key Secondary Endpoints

Key Secondary endpoints were ordered to reflect the most recent FDA Draft Guidance and EMA Final Guideline that prioritizes effects on pathophysiology in EAD, as measured by biomarkers (February, 2018). Conventional analysis will be performed using all available data at the time of success (if applicable), and at 18 months of treatment, regardless of success. An MMRM will be used to compare the combined 10 mg dose group (including biweekly and monthly regimens) with placebo for the key secondary endpoints: (revised per Amendments 09 and 10) The rationale for combining the two 10-mg dose regimens is to account for the loss of subjects positive for *APOE4* in the 10 mg/kg biweekly dose group and the inability to randomize *APOE4* carriers to the 10 mg/kg biweekly group following a Regulatory request by European Health Authorities in July, 2014. The key Secondary endpoint based on clinical status (ADCOMS, CDR-SB, and ADAS-Cog) will be analyzed in subjects with EAD as well as separately within subjects with MCI and mild AD dementia. (revised per Amendment 10)

In addition, as sensitivity analysis, MMRM analysis will be performed for the following treatment comparisons: (revised per Amendment 10)

- Combining 2 high doses (10 mg biweekly + 10 mg monthly), 2 middle doses (5 mg biweekly + 5 mg monthly), and the 2.5 mg biweekly dose, resulting in 3 treatment comparisons with placebo (for dose response) (revised per Amendment 10)
- ED₉₀ dose of BAN2401 versus placebo, where the ED₉₀ dose of BAN2401 will be established by Bayesian analysis at 18 months as described in the next paragraph (revised per Amendment 10)
- By treatment regimen (10 mg biweekly, 10 mg monthly, 5 mg biweekly, 5 mg monthly, 2.5 mg biweekly, placebo) (revised per Amendment 10)
- Combining the top 3 doses (10 mg biweekly, 10 mg monthly, and 5 mg biweekly) versus placebo (revised per Amendment 10)

Change from baseline in the ADCOMS at 18 months will be analyzed, as a sensitivity analysis to the conventional

analysis, using the same Bayesian methodology as that for analysis of change from baseline in the ADCOMS at 12 months, but using the full 18 months of efficacy data with the model projecting to 18 months of treatment. The Bayesian analysis of change from baseline in the ADCOMS at 18 months is positive if the analysis results in an ED₉₀ dose with at least an 80% probability of being better than the placebo by the CSD. The ED₉₀ dose will be identified based on change from baseline in the ADCOMS at the 18 month Bayesian analysis and will be used to compare ED₉₀ dose of BAN2401 and placebo in the above sensitivity analyses for all key secondary endpoint analyses. (revised per Amendments 09 and 10)

Analysis for Other Secondary Endpoints

The same analysis described above for key secondary endpoints will be performed for other secondary endpoints. (revised per Amendment 10)

Analysis for Exploratory Endpoints

The same analysis described above for key secondary endpoints will be performed for exploratory endpoints. (revised per Amendment 10)

The effect of baseline brain amyloid pathophysiology as measured by amyloid PET on change from baseline in clinical status at 12 and 18 months of treatment will be explored using correlation analysis and evaluated using statistical models as appropriate. (revised per Amendment 10)

The relationship between change from baseline in clinical status and change from baseline in brain amyloid pathophysiology at 12 and 18 months of treatment as measured by amyloid PET will be explored by correlation analysis. (revised per Amendment 10)

Change in ADCOMS and its components, ADAS-Cog, CDR-SB, and MMSE across all clinical assessment time points between BAN2401 and placebo in Japanese subjects will be evaluated using the descriptive statistics within Japanese subjects as well as with the overall population. (revised per Amendments 07 and 10)

Extension Phase Part A (revised per Amendments 08, 11, and 19)

An MMRM will be used to analyze the change from baseline secondary efficacy endpoints. Proportion of amyloid positive subjects over time will be summarized. MMRM will also be used to analyze the following exploratory endpoints:

- Change from baseline in the ADCOMS, CDR-SB, ADAS-Cog score, and MMSE score

For each endpoint at a scheduled visit in the Extension Phase, a 90% 1-sided confidence interval will be constructed to test the null hypothesis that the treatment difference between subjects who took placebo in Core Study and those who took 10 mg/kg biweekly in the Core Study is no more than 50% of the treatment difference at the end of Core Study. If the lower limit of this confidence interval is greater than 0, the null hypothesis is rejected. In addition, comparisons between subjects who took placebo at Core Study and those who took 10 mg/kg biweekly in the Core Study will be performed for each endpoint at scheduled visits in the Extension Phase. (revised per Amendment 11)

Time to worsening of CDR global scores will be analyzed on the FAS using Cox regression model. Time to worsening of CDR global score is defined as time from the first treatment in the Extension Phase to worsening of the CDR score (ie, the first worsening in 2 consecutive scheduled visits). For subjects whose CDR scores have not worsened by the end of study, the time to worsening of the CDR score will be censored at the date of last CDR assessment for these subjects. (revised per Amendment 11)

Change from baseline in total hippocampal volume and other biomarkers will be summarized using descriptive statistics at scheduled visits in the Extension Phase. Biomarker and efficacy analysis in the dosing regimen substudy will also be performed similarly by dosing regimen. The details will be included in SAP. (revised per Amendment 17)

Additional analyses and summaries will be performed as appropriate.

Pharmacokinetic and Pharmacodynamic Analyses (Core Study and Extension Phase Part A)**Pharmacokinetics:**

The Safety Analysis Set will be used for individual BAN2401 serum and CSF concentration listings (Core Study only). The PK Analysis Set will be used for summaries of BAN2401 serum and CSF concentrations (Core Study only). (revised per Amendment 11)

A population PK approach will be used to characterize the PK of BAN2401. The effect of covariates (ie, demographics) on BAN2401 PK will be evaluated. The PK model will be parameterized for clearance (CL) and volumes of distribution. Derived exposure parameters such as area under the concentration-time curve (AUC) will be calculated from the model using the individual posterior estimate of CL and dosing history.

Pharmacodynamics:

The PD Analysis Set will be used for the summaries and analyses of CSF biomarkers (Core Study only). (revised per Amendment 11) CSF A β (1-42), t-tau, and p-tau will be assessed and data presented graphically. Baseline levels and changes in t-tau and p-tau will be correlated with changes in CSF A β (1-42), imaging markers, and *APOE4* status.

Summary statistics for CSF biomarkers will be assessed for evidence of a dose relationship.

Pharmacokinetic-Pharmacodynamic:

The PK/PD relationship between CSF biomarker levels (Core Study only) and serum PK parameters or CSF concentrations of BAN2401 will be explored graphically and any emergent relationship will be explored through population PK/PD modeling (revised per Amendment 11). These serum PK parameters include steady state (SS), maximum observed concentrations (C_{max}), and $AUC_{(0-t)}$ derived from the population PK model. The PK/PD relationship between serum PK parameters and CSF concentrations of BAN2401 with other biomarkers may also be explored using similar methods.

Additionally, the relationship between various serum PK parameters or CSF concentrations of BAN2401 (Core Study only) and the ADCOMS at 12, 18, 30, and 42 months, and the relationship between various serum PK parameters or CSF concentrations of BAN2401 (Core Study only) and the change from Baseline for 12, 18, 30, and 42 months in the ADAS-Cog, the CDR, and the MMSE will be explored graphically. (revised per Amendments 08 and 11) Any emergent relationship will be explored through population PK/PD modeling.

The relationship between exposure to BAN2401 and most frequent AEs will also be explored.

Extension Phase Part B (revised per Amendment 19)

No PK or PD analyses will be performed.

Safety Analyses**Core Study**

Evaluations of safety will be performed on the Safety Analysis Set of the Core Study. (revised per Amendment 08) The incidence of AEs (including changes from baseline in physical examination), out-of-normal-range laboratory safety test variables, abnormal ECG findings, out-of-range vital signs, and suicidality (C-SSRS), along with change from baseline in laboratory safety test variables, ECGs, brain MRI, ADAs (screening and neutralizing) and vital sign measurements, will be summarized by treatment group using descriptive statistics.

Extension Phase Part A (revised per Amendments 08, 17, and 19)

Safety analysis will be performed similarly to the Core Study. All safety analyses will be based on Safety Analysis Set of the Extension Phase. The incidence of treatment emergent adverse events (TEAEs), laboratory test variables, ECG findings, vital signs, brain MRI, and ADAs will be summarized using descriptive statistics. Safety analysis in the Dosing Regimen substudy will also be performed similarly by dosing regimen. The details will be included in SAP. (revised per Amendment 17 and 19)

Extension Phase Part B (revised per Amendment 19)

Safety analysis will be performed similarly to the Core Study. All safety analyses will be based on Safety Analysis Set of the Extension Phase Part B. The incidence of TEAEs, vital signs, and brain MRI, will be summarized using descriptive statistics. The details will be included in the SAP. (revised per Amendment 19)

Interim Analyses (Core Study only) (revised per Amendment 11)

An unblinded independent Interim Monitoring Committee (IMC) will provide oversight to ensure that the response adaptive randomization process and IA perform as expected. An independent data analysis group will perform all of the IA and provide the results to the IMC.

Randomization to placebo or 1 of 5 dose arms of BAN2401 will be fixed for the first 196 subjects randomized in the study (4:2:2:2:2:2; placebo [4] to each of the active arms [2 each]). After this initial burn-in, adaptive randomization will begin. Randomization probabilities to each arm will be updated at each IA such that the randomization probability will be increased for the placebo arm and arms that represent the potential target dose (ED₉₀), and simultaneously decreased for other active arms. Subjects who are confirmed *APOE4* positive (*APOE4* hetero- or homozygous) will not be randomized to the 10 mg/kg, biweekly dose. (revised per Amendment 05) Details of the estimation of the randomization probabilities will be presented in the Statistical Analysis Plan.

The study will be monitored for early success and early futility (see [definitions in Study Definitions](#)). The first IA will be conducted when 196 subjects are randomized, again when 250 subjects are randomized, and after each additional 50 subjects until all 800 subjects are randomized. Sites in Japan will randomize at least 40 Japanese subjects, even if early success is declared or the study achieves 800 subjects randomized. In these circumstances, subjects in Japan will be allocated treatment according to the latest (or last) allocation schedule. If the study reaches its maximum of 800 randomized subjects, additional IA will be conducted every 3 months until all subjects complete 12 months of treatment. Only those subjects who were randomized before the target of 800 was met will contribute to these additional IA, except for the full 12 and 18 month Bayesian analyses. The study will be monitored for futility at each IA and for success starting at the 350-subject IA, until the full 12 months of treatment have been completed. (revised per Amendment 09) Each IA will be conducted on data for ADCOMS, which is the derived score optimized to capture AD-related clinical progression. If the efficacy or futility boundary is reached, the IMC will communicate directly with the DSMB members. (revised per Amendment 07) The study may be stopped for safety reasons at any time.

Sample Size Rationale**Core Study****Primary Endpoint - ADCOMS**

The sample size and design characteristics to test the hypothesis under primary objective based on the primary endpoint, the ADCOMS at 12 months, were determined by means of simulations. Extensive trial simulations have shown that a total of 800 subjects will be sufficient to demonstrate that the most likely ED₉₀ dose achieves a CSD from placebo with a probability of at least 95% in the IA and greater than 80% in the final analysis if the trial does not stop for early success. There is at least 80% probability of study success for the dose response scenarios where the treatment was considered to have a clinically meaningful treatment effect. Simulations have also shown that if there is no efficacy at all for any dose, the probability of falsely claiming superiority to placebo is no more than 10.0% assuming a 20% dropout rate.

For each of the 6 treatment groups (5 active dose regimens and placebo), the final number of subjects per group will differ depending on the observed interim treatment responses. The simulation plan will be described in the Appendix section of the Statistical Analysis Plan, which will present further details.

vMRI

The null hypothesis is that there is no difference between active dose and placebo. There are 5 null hypotheses corresponding to 5 active dose regimens. The alternative hypothesis is that at least 1 null hypothesis is false (1-sided). The null hypotheses will be tested using the Dunnett method with 1-sided alpha of 0.05. The statistical power was estimated through simulation for a moderate dose-response assumption that the percent reduction in change from baseline of total hippocampal volume compared to placebo would be 15%, 20%, 25%, 15%, and

20% corresponding to the 5 dose regimens (2.5, 5, and 10 mg/kg biweekly, 5 and 10 mg/kg monthly interval), respectively. The estimated power for actual planned study sample size is 0.764 at 12 months and 0.694 at 18 months assuming an attrition rate of 20% at 12 months and an exponential dropout model. Under a stronger dose-response assumption (ie, the percent reduction in change from baseline of total hippocampal volume compared to placebo is twice as much as that in the moderate dose-response assumption), the estimated power is at least 99% at both 12 and 18 months.

Amyloid PET (Imaging Subgroup)

The null and alternative hypotheses and statistical test are the same as that for vMRI. To estimate the sample size for amyloid PET imaging subgroup at 18 months, a common standard deviation of change from baseline was estimated as 0.4 and a reasonable mean difference between treatment and placebo was estimated as 0.25 standard uptake value ratio (SUVR). The corresponding standard deviation and mean difference at 12 months were estimated as 0.27 and 0.17, respectively. Assuming a moderate dose response that the best dose regimen would achieve a difference of 0.25 (SUVR) and that the 2 middle and 2 low dose regimens would achieve a difference of 0.2 and 0.15 (SUVR), respectively, it would require a total 230 subjects from all 6 arms at 18 months to achieve an 80% power. This sample size took into account possible unequal number of subjects per arm. Under the same attrition rate assumption as that for vMRI, a total sample size of 306 at 12 months is sufficient to obtain 230 subjects at 18 months. The estimated power with 306 subjects at 12 months is approximately 85%. The postbaseline amyloid PET in the imaging subgroup will be planned for the first 306 subjects who have consented and who are still on treatment at 12 months. (revised per Amendments 02 and 07)

Extension Phase Part A and Part B (revised per Amendments 08, 11, and 19)

There is no sample size calculation for the Extension Phase.

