BAN2401 drug product is currently supplied as a sterile aqueous solution containing 10 mg/mL BAN2401, 25 mM sodium citrate/citric acid, 125 mM sodium chloride, and 0.02% (w/v) polysorbate 80 at pH 5.7 in a 10-mL glass vial. This current formulation of the drug product may be progressively phased out as stocks near the end of their shelf life and replaced by a newer formulation containing 100 mg/mL BAN2401. The newer formulation (100 mg/mL BAN2401) was developed to reduce the number of vials of drug product required per dose and to reduce demand for storage space in a pharmacy. The newer (100 mg/mL BAN2401) formulation is supplied as a sterile aqueous solution containing 100 mg/mL BAN2401, 50 mmol/L citric acid, 0.05% (w/v) polysorbate 80, and 350 mmol/L arginine, at pH 5.0, in glass vials containing 5 mL solution. The phasing out of the older formulation will only occur after appropriate regulatory authority approval for the newer formulation has been obtained, and adequate training of any pharmacy staff involved in the preparation of the final drug product for infusion has been completed. The appearance of the 2 different formulations after dilution in normal saline is identical.

Subjects, including those who are confirmed *APOE4* positive (hetero- or homozygous), will be administered the BAN2401 10 mg/kg biweekly dose. For subjects participating in the dosing regimen substudy, BAN2401 10 mg/kg will be administered either at Q4W or Q3M intervals until the end of the study. BAN2401 will be administered in normal saline as 60 minute IV infusions. An infusion system containing a terminal 0.22- μ m in-line filter is required for administration of BAN2401 drug product. (revised per Amendment 17)

EXTENSION PHASE PART B (revised per Amendment 19)

All subjects will be administered the BAN2401 10 mg/kg biweekly dose. For subjects who previously participated in the Dosing Regimen substudy, BAN2401 10 mg/kg will be administered either at the biweekly dose or they may continue with their prior dose of Q4W or Q3M intervals. BAN2401 will be administered in normal saline as 60 minute IV infusions. An infusion system containing a terminal 0.22- μ m in-line filter is required for administration of BAN2401 drug product. (revised per Amendment 19)

Duration of Treatment (revised per Amendments 08, 11, 15, 18, and 19)

Core Study: up to 18 months of treatment.

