- Change from baseline at 12 months in brain amyloid pathophysiology as measured by amyloid PET
- Change from baseline at 12 months on clinical status for the following assessments: ADCOMS, CDR-SB, and ADAS-Cog
- Change from baseline in CSF biomarkers (A β [1-42], t-tau, and p-tau) at 12 months
- Change from baseline in total hippocampal at 6 and 12 months, and in left and right hippocampus, whole brain, and total ventricular volume as measured by vMRI at 6, 12, and 18 months

Exploratory Endpoints:

- Change from baseline in clinical status at time points not analyzed in Key Secondary and Secondary sections for each of the following: ADCOMS, ADAS-Cog, CDR-SB, MMSE, and FAQ

Extension Phase Part A (revised per Amendments 08, 11, 15, 16, 17, and 19)

Primary Endpoint

- Safety assessments will be based on medical review of AE reports and the results of vital sign measurements, ECG, physical examinations, clinical laboratory tests, anti-drug antibody (ADA) test results, and any relevant test of cognitive function to evaluate decline. Additionally, MRI assessments of microhemorrhage, vasogenic edema, and other clinically significant abnormalities will be evaluated.

Secondary Endpoints (revised per Amendment 11)

- Change from baselines in brain amyloid levels as measured by amyloid PET at 3 months (Visit 50 [Extension Week 13], Cohort 1) or 6 months (Visit 57 [Extension Week 27], Cohort 2), 12 months and annually thereafter in the Extension Phase (revised per Amendment 15)
- Change from end of Core Study in brain amyloid levels as measured by amyloid PET at the baseline of Extension Phase
- Proportion of amyloid positive subjects over time

Exploratory Endpoints

- Change from baselines in ADCOMS, CDR-SB, ADAS-Cog, and MMSE at each visit assessed (revised per Amendment 11)
- Time to worsening of CDR global scores, eg, the worsening of global CDR score is defined as an increase from baseline by at least 0.5 points on the global CDR scale on 2 consecutive scheduled visits at which global CDR is measured
- Change from baselines in total hippocampal volume and other biomarkers annually in the Extension Phase. (revised per Amendments 11 and 15)

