- The **OLE Full Analysis Set (OLE-FAS)** is the group of subjects who receive at least 1 dose of study drug during the Extension Phase and who have a baseline assessment and at least 1 postdose efficacy measurement during the Extension Phase Part A. The baseline assessment is defined as the last measurement before 1st dose of BAN2401. (revised per Amendment 17)
- The **OLE Safety Analysis Set** is the group of subjects who receive at least 1 dose of study drug during the Extension Phase Part A. This analysis set is the analysis population used for all safety analyses which will be based on the as-treated principle. (revised per Amendment 17)
- The **OLE PK Analysis Set** is the group of subjects with at least 1 quantifiable BAN2401 serum concentration with a documented dosing history during the Extension Phase Part A.
- The **OLE PD Analysis Set** is the group of subjects who have sufficient PD data to derive at least 1 PD parameter during the Extension Phase Part A.

Extension Phase Part B (revised per Amendment 19)

- The **OLE Safety Analysis Set** is the group of subjects who receive at least 1 dose of study drug during the Extension Phase Part B. This analysis set is the analysis population used for all safety analyses which will be based on the as-treated principle.

Similar analysis sets will be defined for the dosing regimen substudy. The details will be included in the statistical analysis plan (SAP). (revised per Amendment 17)

Efficacy Analyses (revised per Amendment 19)**Core Study**

In this Phase 2 dose-finding study of BAN2401 for the treatment of EAD, response adaptive randomization will be used to allocate subjects to placebo or 1 of the 5 active dose regimens with the goal of characterizing the dose response. The study will be monitored for early success and early futility. If the study continues to randomize subjects after futility is declared, it will be considered a failed study. (revised per Amendment 01)

Key definitions relevant to the Bayesian aspects of the adaptive design are given below.

Study Definitions

Clinically Significant Difference (CSD): The CSD used in the adaptive model relative to the change from baseline over time for placebo in the ADCOMS. The CSD for this study represents an approximate 25% reduction compared to placebo in the progression of AD as measured by the ADCOMS.

Maximum Effective Dose (d_{Max}): The dose that achieves the greatest treatment effect

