- Change from end of Core Study in brain amyloid levels as measured by amyloid PET at the baseline of Extension Phase
- Proportion of amyloid positive subjects over time

Exploratory Endpoints

- Change from baselines in ADCOMS, CDR-SB, ADAS-Cog, and MMSE at each visit assessed
- Time to worsening of CDR global scores, eg, the worsening of global CDR score is defined as an increase from baseline by at least 0.5 points on the global CDR scale on 2 consecutive scheduled visits at which global CDR is measured
- Change from baselines in total hippocampal volume and other biomarkers annually in the Extension Phase (revised per Amendment 15)
- Describe the characteristics, comorbidities, treatments, associated costs for subjects with EAD, and study partner burden up to 5 years before study enrollment, for the duration of the Core Study, the duration of the period between the end of the Core Study and the Extension Baseline (if applicable), the duration of the Extension Phase (if applicable), and for up to 3 years after the end of the Core Study or Extension Phase (where applicable) (revised per Amendment 16)

Dosing Regimen Substudy Endpoints (revised per Amendment 17)

- Change from substudy baseline in brain amyloid levels as measured by amyloid PET
- Change from substudy baseline in plasma A β 42/40 ratio and plasma p-tau181
- Change from substudy baseline in ADCOMS, CDR-SB, ADAS-Cog, and MMSE at each visit assessed
- Safety assessments including, but not limited to, AEs, vital signs, ECG, physical examinations, clinical laboratory tests, anti-drug antibody (ADA). MRI assessments of microhemorrhage, vasogenic edema, and other clinically significant abnormalities
- Population PK parameters of BAN2401 in serum, including but not limited, to AUC, C_{av}, Correlation of PK exposure with biomarkers, safety parameters, and efficacy

ANALYSIS SETS

- The **OLE Full Analysis Set (OLE-FAS)** is the group of subjects who receive at least 1 dose of study drug during the Extension Phase and who have a baseline assessment and at least 1 postdose efficacy measurement during the Extension Phase Part A. The baseline assessment is defined as the last measurement prior to first dose of BAN2401 in the Extension Phase Part A. (revised per Amendments 17 and 19)

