- The **OLE Safety Analysis Set** is the group of subjects who receive at least 1 dose of study drug during the Extension Phase Part A. This analysis set is the analysis population used for all safety analyses which will be based on the as-treated principle. (revised per Amendments 17 and 19)
- The **OLE PK Analysis Set** is the group of subjects with at least 1 quantifiable BAN2401 serum concentration with a documented dosing history during the Extension Phase Part A. (revised per Amendment 19)
- The **OLE PD Analysis Set** is the group of subjects who have sufficient PD data to derive at least 1 PD parameter during the Extension Phase Part A. (revised per Amendment 19)

Similar analysis sets will be defined for the Dosing Regimen substudy. The details will be included in the SAP. (revised per Amendment 17)

EFFICACY ANALYSES

An MMRM will be used to analyze the change from baseline secondary efficacy endpoints. Proportion of amyloid positive subjects over time will be summarized.

An MMRM will also be used to analyze the following exploratory endpoints (revised per Amendment 17):

- Change from baseline in the ADCOMS, CDR-SB, ADAS-Cog score, and MMSE score

For each endpoint at a scheduled visit in the Extension Phase, a 90% 1-sided confidence interval will be constructed to test the null hypothesis that the treatment difference between subjects who took placebo in Core Study and those who took 10 mg/kg biweekly in the Core Study is no more than 50% of the treatment difference at the end of Core Study. If the lower limit of this confidence interval is greater than 0, the null hypothesis is rejected. In addition, comparisons between subjects who took placebo at Core Study and those who took 10 mg/kg biweekly in the Core Study will be performed for each endpoint at scheduled visits in the Extension Phase.

Time to worsening of CDR global scores will be analyzed on the FAS using Cox regression model. Time to worsening of CDR global score is defined as time from the first treatment in the Extension Phase to worsening of the CDR score (ie, the first worsening in 2 consecutive scheduled visits). For subjects whose CDR scores have not worsened by the end of study, the time to worsening of the CDR score will be censored at the date of last CDR assessment for these subjects.

Change from baseline in total hippocampal volume and other biomarkers will be summarized using descriptive statistics at scheduled visits in the Extension Phase.

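### Synopsis and Appendix 4 define the Extension baseline differently; taken literally, the synopsis version reverses the Core placebo versus 10 mg/kg biweekly comparison on the clinical scales

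*Protocol*

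**What the plan says.** Two current passages define baseline for the same set, the OLE-FAS.

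- Synopsis (Section 2), Analysis Sets, Extension Phase Part A: "The baseline assessment is defined as the last measurement before 1st dose of BAN2401". No phase is named.
- Appendix 4, Analysis Sets: "The baseline assessment is defined as the last measurement prior to first dose of BAN2401 in the Extension Phase Part A".

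The efficacy text for Part A, in the synopsis and again in Appendix 4, plans "comparisons between subjects who took placebo at Core Study and those who took 10 mg/kg biweekly in the Core Study" at scheduled Extension visits. It also sets a retention test: the null is that the difference between these two groups "is no more than 50% of the treatment difference at the end of Core Study", and for this "a 90% 1-sided confidence interval will be constructed". Neither place says which baseline these comparisons use. The exploratory clinical endpoint is worded "Change from baselines in ADCOMS, CDR-SB, ADAS-Cog, and MMSE at each visit assessed", with a plural that is not explained.

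Time to worsening of the global CDR runs from the first Extension treatment for everyone. Worsening itself is a rise of at least 0.5 points from baseline on two consecutive scheduled visits.

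**The concern.** A subject on active drug in the Core Study had the first BAN2401 dose at Core Day 1. A Core-placebo subject has it at the first Extension dose. The synopsis sentence, taken at its word, therefore gives the two compared groups different time origins. The synopsis, Duration of Treatment, gives "Core Study: up to 18 months of treatment", so for Core completers the origins lie at least 18 months apart. Any off-drug interval before the Extension is added, and Section 9.1.3 admits subjects who had finished the Core Study earlier.

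On a scale that worsens over time, the Core-active group then carries its whole Core decline into the change score while the placebo group carries none of it. A real benefit can come out as harm.

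The CDR endpoint is touched as well. A Core-active subject whose global CDR rose by 0.5 during the Core Study already meets the size of increase at Extension time zero. A Core-placebo subject with the same history does not.

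**Working it through.** The protocol states no expected Extension difference, power or sample size, so there is no figure to reproduce. The check is arithmetic on mean changes.

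**Inputs from the protocol**
- Core treatment: 18 months (synopsis, Duration of Treatment).
- ADCOMS at 18 months, 10 mg/kg biweekly: 30% less decline than placebo, P-value 0.034 (Section 7.2.1.2). The same section gives 47% for ADAS-Cog and 26% for CDR-SB. The clinically significant difference is about 25% (Section 9.7.1.6).
- PET planning differences: 0.17 SUVR at 12 months and 0.25 at 18 months (Section 9.7.1.9).

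**Assumptions**
- Worsening counts as positive, and P is the Core-placebo decline over 18 months.
- Off-drug gap g is 0 to 24 months, because its length is not given. Both groups decline at P/18 per month during it, so G = g x P/18.
- Both groups have the same open-label change E at any Extension visit.

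**Clinical scales, active minus placebo (negative = benefit)**

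| Baseline | Formula | g = 0 | g = 12 | g = 24 |
|---|---|---|---|---|
| Core, both groups | (0.70P + G + E) - (P + G + E) | -0.30P | -0.30P | -0.30P |
| Synopsis, literal | (0.70P + G + E) - E | +0.70P | +1.37P | +2.03P |
| Appendix 4 | E - E | 0 | 0 | 0 |

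E cancels, so the result does not depend on the visit or on the shared slope. The synopsis value always equals the common-Core value plus the placebo group's decline from Core baseline to Extension baseline.

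With other Core slowing and no gap, the synopsis value is 1 - s in units of P: +0.75P at 25%, +0.74P at 26%, +0.53P at 47%. It reaches zero only if the active group did not decline at all in the Core Study.

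For scale: if P = 0.034 is two-sided, z = 2.12 and the implied Core standard error is 0.30P / 2.12 = 0.14P. The shift of 1.0P is about 7 times that.

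**Retention test.** Take the contrast as benefit minus half the end-of-Core benefit, with no gap.
- Core baseline: 0.30P - 0.15P = +0.15P.
- Synopsis: -0.70P - 0.15P = -0.85P.
- Appendix 4: 0 - 0.15P = -0.15P, although the benefit is fully maintained in this scenario.

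**Amyloid PET, Extension month 12.** Assume Core-placebo subjects fall by 0.17 in the Extension and Core-active subjects stay level.
- Flat placebo in the Core, no re-accumulation: common Core baseline -0.25 + 0.17 = -0.08; synopsis -0.25 + 0.17 = -0.08; Appendix 4 0 + 0.17 = +0.17 SUVR.
- Placebo rise of 0.05 in the Core only: common Core baseline -0.08, synopsis -0.03.
- Placebo rise of 0.05 and re-accumulation of 0.05: Core-active change is -0.25 + 0.05 + 0.05 = -0.15. Common Core baseline is -0.15 - (0.05 - 0.17) = -0.03; synopsis is -0.15 + 0.17 = +0.02.

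The placebo rise is what shifts the PET estimate. Re-accumulation brings the true difference nearer zero, so that a small shift can change the sign.

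**The case against.** The strongest reply is that this is an editorial slip. The synopsis sentence sits inside a set-membership definition that already speaks of Extension dosing, so its first dose may be shorthand for the first Extension dose. Appendix 4 says exactly that, carries the later amendment tag (19 as well as 17), and is named in Section 9.1.3 as the full description of Part A. That is probably the intent. It does not remove the problem: both sentences are current, they differ, and nothing says which governs. If Appendix 4 governs, the between-group comparisons still have no stated baseline.

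A second reply is that the plural in the endpoint wording hints at more than one baseline, that the retention null is anchored to the end-of-Core difference, and that an analysis plan may assign baselines to comparisons. This has force. A reader might infer that under Appendix 4 retention of half the benefit can never be shown. The documents do not support that. It would require the OLE-FAS baseline to govern the retention test, which is not stated, and the zero difference arises from parallel Extension slopes rather than from the definition alone.

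A reader might also infer that about 71% of subjects change origin, from 609 of 854 treated in Table 2. That counts all five active arms of the Core Study, not Extension entrants in the two groups compared. In Table 2 those groups are 161 and 245, so 161/406 or about 40%, before any loss on the way into the Extension. The Extension mix is not given.

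Finally, the stakes are limited. The Part A primary endpoint is safety, the clinical scales are exploratory, there is no Extension sample size, and Appendix 4 elsewhere disclaims hypothesis testing for efficacy variables. That stands.

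**Conclusion.** The concern holds in a bounded form. The protocol defines the OLE-FAS baseline in two incompatible ways. Used literally for the Core placebo versus 10 mg/kg biweekly comparison, the synopsis version reverses the sign on ADCOMS, CDR-SB, ADAS-Cog and MMSE: +0.70P instead of -0.30P with 30% Core slowing, equal open-label slopes and no gap, and further off with a gap. It also shifts the reference score for CDR worsening; the CDR clock itself is the same for everyone.

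It would be tempting to extend the reversal to every Extension endpoint. Amyloid PET, the only change-from-baseline efficacy measure ranked secondary in Part A, does not reverse under the synopsis wording on the planning values. It does so only with assumed drift, here 0.05 SUVR of placebo rise together with 0.05 of re-accumulation.

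The Appendix 4 wording is sound for within-Extension change but, if carried into the retention test, would fail to show a fully maintained benefit under parallel progression. This should be fixed, but it is not critical: the Core primary and key secondary analyses and the Part A safety endpoint are unaffected.

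**What to change.** 1. In the synopsis, add the Part A qualifier so that the OLE-FAS baseline matches Appendix 4. Use that Extension baseline for set membership, within-Extension change and the reference score for CDR worsening.
2. In the Part A efficacy text of both the synopsis and Appendix 4, state that the placebo versus 10 mg/kg biweekly comparisons and the 50% retention test use change from Core baseline in both groups.
3. Say which baselines the plural in the endpoint wording refers to.

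The cost is wording only. Core and Extension baseline assessments are already scheduled in Tables 7 and 13, so no new data are needed.
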